14.1 The Objectives of the IA

The objective of the IA is to determine whether the study should be stopped early due to futility. The IA does not involve the possibility of stopping early for success; since there is no possibility of stopping early for success, there is no possibility of committing a Type 1 statistical error at the interim analysis, and hence no inflation of the Type 1 statistical error will occur at the conclusion of the study. The final primary endpoint analysis will be conducted with a 2-sided p-value threshold of 0.05 for determining study success (no penalty for having conducted the interim analysis with futility stopping rule).

14.2 Efficacy and Safety Variables

The efficacy variable of interest for the IA is the WOMAC A1 pain score change from baseline difference between treatment groups (MONOVISC minus Saline), expressed as an improvement.

The assessment of Safety is not an explicitly stated objective, however, sufficient safety data is required to inform a decision concerning membership in the IA PP Analysis Set at Week 26.

14.3 Timing and Frequency of the IAs

A single IA of the primary endpoint will be conducted after 74 subjects in the MONOVISC arm and 37 patients in the saline arm have entered the IA PP Analysis Set at 26 Weeks.

14.4 Analysis Sets for the IA

Two analysis sets will be utilized in the IA, the IA PP Analysis Set at 26 Weeks and the IA AT Analysis Set at 26 Weeks.

14.5 Data Cut Criteria

The IA results will inform decision-making regarding study continuation. Therefore, all data required to conduct the analysis must be clean. As the study will be ongoing at the time of the IA and data will continue accrue, a mechanism to ensure only clean data are analyzed is required. A filtering algorithm will be implemented to restrict the data analyzed to include only data reported for subjects included in union of the IA AT Analysis Set at 26 Weeks and the IA PP Analysis Set at 26 Weeks. In addition to the WOMAC data, all data required to make the determination of inclusion into the IA PP Analysis Set at 26 Weeks is required.

14.6 Analysis Plan

The analysis will consist of an assessment of the 26 Week improvement of the MONOVISC group over the Saline group in mean WOMAC A1 walking pain score. This analysis will be conducted on the IA PP Analysis Set at 26 weeks and also the IA AT Analysis Set at 26 Weeks. There is no reliance on statistical significance (p-values or confidence intervals) as the comparison is made to a predefined futility boundary.

Analysis will be conducted by a team of qualified employees from within DePuy Synthes Mitek Sports Medicine BSDM department who will be designated to conduct the IA. Members of this team will not be otherwise associated with the conduct of the study and the analysis will be conducted in a separate area with access granted only to those designated as unblinded.

14.7 Possible Decisions or Actions Based on the IA Results

An early stopping rule for futility will be implemented in which the study will be terminated if the WOMAC A1 pain score change from baseline difference (MONOVISC minus Saline) is less than 0.4 in both the IA PP Analysis Set at 26 Weeks and the IA AT Analysis Set at 26 Weeks. All Patients already enrolled in the study at the time of the interim analysis will be followed to 26 weeks. No additional enrollment will be conducted. If this difference is greater than 0.4 (which favors MONOVISC) in either the IA PPP Analysis Set at 26 Weeks or the IA AT Analysis Set at 26 Weeks, the study will continue to completion.

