	
 • Pain improvement from baseline at the 2, 4, 8, 16 and 26 week time points as measured by WOMAC A (pain) score. • Total WOMAC (pain, function, stiffness) score at the 2, 4, 8, 16 and 26 week time points. • Improvement from baseline in Total WOMAC (pain, function, stiffness) score at the 2, 4, 8, 16 and 26 week time points. • OMERACT-OARSI responder rate at the 2, 4, 8, 16 and 26 week time points. • Patient Global Assessment (PGA) at the 2, 4, 8, 16, and 26 week time points. • SF-12 outcomes at study defined time-points • Rescue medicine consumption (acetaminophen) from baseline through week 26 
Safety:
 
 • Comparison of adverse events between MONOVISC and saline groups.
Sample Size Justification:	
A sample size was calculated that would provide 80% power for demonstrating superiority in WOMAC A1 (walking pain) change from baseline at 26 weeks; it is anticipated that there will be a difference of at least 0.6 NRS between MONOVISC and Saline subjects, and that both groups will have a standard deviation of 2.2 NRS. The required sample size is 477 with 2:1 randomization (318 MONOVISC / 159 Saline). This was increased to 374 MONOVISC / 186 Saline (560 patients total) to accommodate up to 15% attrition.

Interim data analysis:	
The primary endpoint will be assessed after 74 MONOVISC and 37 Saline Subjects have completed their 26 week visit. The study will be terminated if the separation (point estimate) between MONOVISC and saline is less than 0.4 NRS for the primary endpoint of WOMAC A1 walking pain change from baseline in both the Per Protocol Analysis Set for the 26 week interval and the As Treated Analysis Set for the 26 week interval. Enrollment will continue throughout the time preceding and during the interim analysis.

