6.0 Study Design

This study is a prospective, multi-center, double-blinded, randomized, controlled, superiority study comparing intra-articular injections of MONOVISC High Molecular Weight Hyaluronan with intra-articular injections of physiologic saline. The study will take place at up to 40

investigational sites, primarily in the United States. Additional sites may be added in Canada and/or Europe. Subjects will be randomized through a 2:1 schema to receive either two (2) injections of 4 ml of MONOVISC, separated by 1 month (active treatment), or two (2) monthly injections of 4 ml of saline, separated by 1 month (control treatment).

Subjects will return for follow-up visits at 2, 4, 8, 16, and 26 weeks after the first injection.

The primary endpoint will be pain during walking (WOMAC A1) change from baseline at the 26 week time point.

An interim analysis of the primary endpoint will be conducted after 74 MONOVISC and 37 saline subjects have received both injections of MONOVISC or saline and completed their per protocol 26 week follow up visit. A stopping rule for futility will be implemented, such that the study will be terminated if the improvement of MONOVISC over saline (change from baseline) is less than 0.4 on a 10 point Numerical Rating Scale (NRS) in both the Per Protocol Analysis Set for the 26 week interval and the As Treated Analysis Set for the 26 week interval. If the improvement of MONOVISC over saline (change from baseline) is more than 0.4 NRS in either of these analysis sets, the study will continue to completion.

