11.1 Study Design

This study is a prospective, multi-center, double-blinded, randomized controlled trial comparing the treatment group (MONOVISC) to a control (Saline) for the purpose of demonstrating superiority. It is planned that a total of N=560 subjects will be enrolled using a 2:1 randomization (374 MONOVISC and 186 Saline). An interim analysis of the primary endpoint will be conducted after 74 patients in the MONOVISC arm and 37 patients in the Saline arm have completed their 26 week per protocol follow up visit. The study will be terminated if the mean WOMAC A1 pain change from baseline difference (MONOVISC minus Saline) is less than 0.4 in both the Per Protocol Analysis Set for the 26 week interval and the As Treated Analysis Set for the 26 week interval. If this difference is greater than 0.4 in favor of MONOVISC in either the Per Protocol Analysis Set for the 26 week interval or the As Treated Analysis Set for the 26 week interval, the study will continue to completion. Enrollment will continue throughout the time preceding and during the interim analysis.

Further description of the study design can be found in Section 6.0 above.

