11.3 Levels of Significance

Unless otherwise stated, confidence intervals will be 2-sided 95% confidence intervals, and *p*-values will also be 2-sided; *p*-values below 0.05 will be deemed to be statistically significant. Unless otherwise stated, there will be no adjustment of significance levels because of testing multiple hypotheses.

A primary endpoint interim analysis will be conducted after 74 patients in the MONOVISC arm and 37 patients in the saline arm have completed their 26 week follow-up visit to determine whether or not to stop the trial early for futility. This analysis will be based solely on the primary efficacy endpoint, and the trial will stop early if the mean WOMAC A1 pain difference (MONOVISC minus Saline) change from baseline is less than 0.4 in both the Per Protocol Analysis Set for the 26 week interval and the As Treated Analysis Set for the 26 week interval. Since this interim analysis does not have an early stopping rule for success, the final primary endpoint analysis will be conducted with a 2-sided p -value threshold of 0.05 for determining study success (no penalty for having conducted the interim analysis with futility stopping rule). Subject enrollment will continue during the interim analysis period.

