11.9 Sample Size Justification

The sample size was determined based on the primary endpoint, which is a superiority comparison of WOMAC A1 pain change from baseline at 26 weeks for MONOVISC Subjects compared to Saline Subjects. Although it is planned to conduct the primary endpoint analysis with a longitudinal model, and to compare the WOMAC A1 pain change from baseline adjusted means at 26 weeks from this longitudinal model, the sample size was established based upon estimates for a t-test comparison of 26 week means for simplicity. Specifically, it is anticipated that the mean difference in WOMAC A1 pain change from baseline means will be at least 0.6 (where the mean for MONOVISC subjects is less than the mean for Saline Subjects), and that the standard deviation in WOMAC A1 pain change from baseline at 26 weeks will be approximately 2.2 in both groups. This standard deviation of 2.2 is consistent with published studies by Spitzer (2010) and Qvistgaard (2006); also, 2.2 is approximately $\frac{1}{4}$ of the maximum anticipated range of WOMAC A1 pain change from baseline, which would be an estimate of the standard deviation from data which are normally distributed. Using a two-tailed t-test and assuming a 2:1 randomization, the required sample size to yield 80% statistical power was estimated to be 318 MONOVISC and 159 Saline. With an anticipated attrition rate of 15%, the total study population was increased to be 560 patients (374 MONOVISC, 186 Saline). The sample size estimate was calculated with the following SAS code:

SAS Code for Power Estimation:
WOMAC A pain at 26 weeks

```
proc power;
  twosamplemeans
  meandiff= .6
  stddev=2.2
  groupweights=(2 1)
  power= .8
  alpha=0.05
  sides=2
  ntotal=.;
run;
```

The primary efficacy endpoint analysis will be conducted on the modified intent treat (MITT) Analysis Set with the handling of missing data at 26 weeks as described in Section 11.5 above. A supportive analysis will be conducted on the Per Protocol Analysis Set for Longitudinal Analysis.

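### The stated 80% power leaves out the mandatory futility rule; with the rule followed, power at 318/159 is about 59% to 72% over PP/AT ratios of 1.0 to 0.5

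*SAP*

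**What the plan says.** **Power.** The Protocol 1.0 summary states: "A sample size was calculated that would provide 80% power for demonstrating superiority" on the week-26 change in WOMAC A1. Protocol 11.9 says that "the required sample size to yield 80% statistical power was estimated to be 318 MONOVISC and 159 Saline", and SAP 12 repeats this. The inputs are a difference of 0.6, SD 2.2, a two-sided 5% level and 2:1 allocation. The power code printed in Protocol 11.9 is a fixed-sample two-sample comparison with no interim look. Both sections disclose one simplification: a t-test stands in for the longitudinal model.

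**Futility rule.** Protocol 1.0: "The study will be terminated if the separation (point estimate) between MONOVISC and saline is less than 0.4 NRS". Protocol 6.0 and SAP 4: "such that the study will be terminated if the improvement of MONOVISC over saline (change from baseline) is less than 0.4". Protocol 11.1: "The study will be terminated if the mean WOMAC A1 pain change from baseline difference (MONOVISC minus Saline) is less than 0.4 in both" sets. Protocol 11.3: "the trial will stop early if the mean WOMAC A1 pain difference (MONOVISC minus Saline) change from baseline is less than 0.4 in both" sets. Protocol 11.11 and SAP 14.7 use the same mandatory form: "the study will be terminated if the WOMAC A1 pain score change from baseline difference (MONOVISC minus Saline) is less than 0.4 in both" sets. SAP 14.3 sets the look at 74 MONOVISC and 37 saline subjects in the PP set. SAP 14.6 says that only the point estimate counts, and SAP 14.2 expresses the difference as an improvement, so a positive value favours MONOVISC.

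**After a stop.** SAP 14.7: "All Patients already enrolled in the study at the time of the interim analysis will be followed to 26 weeks". It does not say whether those patients are then tested for success.

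**Error rates.** Protocol 11.3 and SAP 14.1 explain why the final 5% level needs no adjustment. Neither mentions type II error.

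**The concern.** A futility rule cannot inflate type I error, but a binding one always costs some power. How much depends on how early the look is and how close the boundary lies to the planned effect. Here the boundary is two thirds of the planned effect (0.4 against 0.6), and the PP estimate is based on 111 of the 477 evaluable subjects in the calculation. A trial whose treatment works exactly as planned therefore has a sizeable chance of being stopped. If that loss is material, the sponsor, the IRBs and FDA are reading a power figure that the design as written does not deliver.

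**Working it through.** **Inputs.** Difference 0.6, SD 2.2, 318/159 and 374/186 (Protocol 11.9, SAP 12); interim PP 74/37 (SAP 14.3); boundary 0.4 in both sets (SAP 14.7); PP is a subset of AT (SAP 11). The PP/AT ratio *r* is not in the documents, so it is varied.

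**1. The plan's own figure.** SE(final) = 2.2 × √(1/318 + 1/159) = 0.2137, and 0.6/0.2137 = 2.81. Normal approximation: Φ(2.81 − 1.96) = 80.2%. The exact noncentral t gives 80.02%. The stated 80% is correct for a trial with no interim look.

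**2. The interim look.** SE(PP) = 2.2 × √(1/74 + 1/37) = 0.443. The planned effect lies (0.6 − 0.4)/0.443 = 0.45 standard errors above the boundary.

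**3. Power with the rule, a stop counted as no success.** The interim AT set has 74/*r* and 37/*r* subjects. The PP, AT and final estimates are nested, so the covariance of a smaller with a larger set is the variance of the larger.

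- P(stop) = P(D_PP < 0.4 and D_AT < 0.4)
- Power = P(no stop and D_final > 1.96 × 0.2137 = 0.419)

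For *r* = 1, P(stop) = Φ(−0.45) = 32.6%. The correlation of the interim and final estimates is 0.2137/0.443 = 0.48. Power is 59.4%, so 80.2 − 59.4 = about 21 trials in 100 are stopped that would have succeeded.

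| PP/AT | Interim AT (111/r) | P(stop) | Power, 318/159 | Power, 374/186 all evaluable |
|---|---|---|---|---|
| 1.0 (limit) | 111 | 32.6% | 59.4% | 61.9% |
| 0.85 (assumed) | 131 | 26.2% | 64.6% | 67.5% |
| 0.75 (assumed) | 148 | 23.9% | 66.5% | 69.5% |
| 0.5 (assumed) | 222 | 18.4% | 71.5% | 74.7% |
| no rule | – | – | 80.2% | 85.9% |

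Simulated individual data analysed with a pooled t-test gave 59.2%, 66.4% and 71.5% at ratios 1.0, 0.75 and 0.5 for 318/159.

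**4. If the patients followed after a stop were tested at 0.05.** Assume even accrual of 560 over 30 months (560/30 = 18.67 per month) and 15% attrition. The interim set is complete at month 111/(*r* × 0.85 × 18.67) + 6, which is month 13.0, 14.2, 15.3 and 20.0 for the four ratios. Evaluable patients at that point = month × 18.67 × 0.85 = 206, 226, 243 and 317. Each month of lag before enrollment ends adds 18.67 × 0.85 = 15.9. The lag is not in the documents. Power at 318/159:

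| Lag (assumed) | PP/AT 1.0 | 0.85 | 0.75 | 0.5 |
|---|---|---|---|---|
| 0 months | 63.2% | 67.2% | 68.9% | 73.8% |
| 3 months | 66.6% | 69.9% | 71.5% | 75.8% |
| 6 months | 70.0% | 72.6% | 73.9% | 77.8% |

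**The case against.** **Both sets must fall below 0.4, so the rule is lenient.** This is already in the calculation. Because PP sits inside AT, the two estimates are strongly correlated and the second condition helps only in part. At 318/159 the loss disappears only when the interim AT set is about as large as the whole final sample (111/477, a ratio of about 0.23).

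**PP = AT is unrealistic.** This stands. Acetaminophen within 48 hours of a visit is the documents' own example of a reason to leave the PP set, and acetaminophen is the permitted rescue drug. A reader might infer from the 59% that this is the trial's power. The documents do not support that; it is the limiting value, the only one that needs no assumed ratio.

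**Counting a stop as failure is the least favourable convention.** This also stands. SAP 14.7 follows enrolled patients to week 26, and the decision criterion in Protocol 11.7 and SAP 10 makes no exception for a stopped trial. Protocol 1.0, 11.1 and 11.3 let enrollment continue during the interim analysis, and SAP 14.5 requires clean data first, so zero lag is the low end. A reader might infer that power stays below 80% whatever is done after a stop. That is shown here only for 318/159 in the cases tabulated. With 374/186 all evaluable, a low ratio and a few months' lag, power can come to about 80% or slightly more, depending on how attrition is counted, against 85.9% without the rule.

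**The rule may be meant as guidance.** Protocol 10.2 allows rather than requires discontinuation, and SAP 14.5 says the results feed into a decision. But Protocol 10.2 refers back to Section 6, where the stop is mandatory, and no section calls the rule non-binding.

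**The final analysis is a longitudinal model.** True, but the stated 80% rests on the same t-test, so like is compared with like.

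**Conclusion.** The concern holds. The 80% is correct arithmetic for a single-stage test, but it is not the power of the design described, because the mandatory futility rule is left out and the omission is not disclosed. At a true 0.6 and 318/159, following the rule takes power to between about 59% (PP = AT) and 71.5% (PP/AT 0.5) if a stop is not a success. If the followed patients were tested, it would be about 63–74%, 67–76% and 70–78% at lags of 0, 3 and 6 months over the same ratios.

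These figures assume the same effect and SD in the PP, AT and final sets. Setting the PP effect to 0.5 or 0.7 instead, with a stop counted as no success, gives 62.6% or 67.4% at ratio 0.85 and 64.7% or 68.9% at 0.75, so the conclusion does not depend on that. The ratio, accrual pattern, attrition timing and lag are assumptions.

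A reader might also infer that the sample size was miscalculated, that the 0.4 boundary is wrong, or that type I error is affected. None of these follows. The plan anticipates a difference of at least 0.6, and a sponsor may knowingly accept the loss of power in exchange for an early exit. The defect is that the documents do not state it.

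**What to change.** In Protocol 1.0 and 11.9 and SAP 12, restate the power with the futility rule applied. Give the probability of stopping at a true 0.6, the assumed PP/AT ratio at the interim, and how a stopped trial is counted, including whether the patients followed to week 26 under SAP 14.7 are tested.

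Alternatively, state that the rule is non-binding, reconcile Protocol 10.2 and SAP 14.5 with Protocol 6.0 and SAP 14.7 (and the parallel statements in Protocol 1.0, 11.1, 11.3, 11.11 and SAP 4), and label the 80% as power without the rule.

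Either route costs a short calculation and a wording change. No change to the boundary, sample size or conduct is part of this fix.

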14.8 Statistical Approach for Modifying the Study Design

Not Applicable

15 List of Tables, Figures, and Subject Data Listings

The document which contains the planned presentation shells (tables, figures and listings) as well as further detail on scoring algorithms for the patient reported outcomes will be created prior to final database lock, and will be called
15-MVH-01 MONOVISC HIP Shells v1.0.

